Participants will not be blinded as to their study condition because participants in the incentive intervention cannot be blind to that intervention.

d. Justification of why participants will not receive routine care or will have current therapy stopped.

All participants will receive the best HIV medical and appropriate referrals to other care that is available in their respective HIV medical clinics. Participation in this study will not limit their access to the highest quality medical care that is available in their medical clinics.

e. Justification for inclusion of a placebo or non-treatment group.

There is not a placebo or non-treatment group in this study.

f. Definition of treatment failure or participant removal criteria.

Participants will be removed from the study if they threaten the safety of the research staff or other research participants.

g. Description of what happens to participants receiving therapy when study ends or if a participant's participation in the study ends prematurely.

Participants will continue to receive HIV medical care as long as that care is available in the medical clinic that they attend.

5. Inclusion/Exclusion Criteria

Applicants will be accepted if they: a) are ≥ 18 yrs old; b) have been diagnosed with HIV for at least 12 weeks; c) have a detectable viral load (>200 copies/mL); and d) are not currently receiving HIV medical care or have been in HIV medical care for at least 12 weeks. Applicants will be ineligible if they a) report current suicidal or homicidal ideation; or b) have a severe psychiatric disorder.

6. Drugs/ Substances/ Devices

NA

a. The rationale for choosing the drug and dose or for choosing the device to be used.

NA

b. Justification and safety information if FDA approved drugs will be administered for non-FDA approved indications or if doses or routes of administration or participant populations are changed.

NA

c. Justification and safety information if non-FDA approved drugs without an IND will be administered.

Date: July 28, 2014

Principal Investigator: [name]

Application Number: IRB00044740

7. Study Statistics

We will compare the Incentive and Usual Care Control groups on primary, secondary and economic measures. To preserve statistical power and minimize the likelihood of false conclusions, we identified one primary biological outcome measure and a limited number of secondary and economic measures. Each measure is associated with a *Specific Aim*.

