Specific Aim. Assess the effectiveness of the incentive intervention for decreased or undetectable viral loads in promoting retention in HIV medical care. We will assess whether the participant attended at least 2 medical visits per year (Mugavaro et al. 2012; Y/N each year based on self-report and medical records).

Specific Aim. Assess the effectiveness of an empirically-based incentive intervention in promoting undetectable levels of viral loads, maintenance of antiretroviral prescriptions, consistent adherence to antiretroviral therapy, and retention in HIV care after the incentive intervention is discontinued. We will assess measures described above but at the two 6-month assessments during the year after the intervention ends.

Moderator Analysis Measures

Specific Aim. Determine if drug (cocaine or opiate) dependence, alcohol dependence, depression, health literacy, and impulsivity assessed at intake moderate viral load suppression and response to the incentive intervention. A dichotomous value (Y/N) for cocaine, opiate and alcohol dependence will be used as assessed by the CIDI. The total score on the TOFHLA will be used to assess health literacy. The total score on the Beck Depression Inventory will be used to assess depression. Log transformed k for each participant on the delay discounting task will be used to assess impulsivity.

Mediator Analysis Measures

Specific Aim. Determine if antiretroviral medication adherence as assessed by qualitative HRMS blood tests of 15 antiretroviral medications mediates the effect of the incentive intervention on viral load suppression. We will assess mediating effects of medication adherence as assessed by qualitative blood testing on viral load using the method of Baron and Kenny (1986) as described below.

Economic Outcome Measures

Specific Aim. Assess the costs of HIV medical care for Usual Care and Incentive groups. We will assess the total cost per participant of both study interventions including cost of the incentive program (see below). We expect that Incentive group costs will be higher relative to the Usual Care due to the incentive program and because we expect that the Incentive participants will have greater treatment engagement.

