Specific Aim. Assess the cost-effectiveness of the empirically-based incentive intervention for undetectable viral loads. We will assess incremental cost-effectiveness ratio (ICER) by dividing the difference in costs of two interventions by the difference in effects of the two interventions during the 2-year intervention evaluation period on viral load suppression (see below). The ICER can be interpreted as dollars spent per unit of desired outcomes gained. The Incentive Intervention should yield a better ICER.

Specific Aim. Assess the cost-benefit of empirically-based incentive intervention for undetectable viral loads. We will perform a Cost-Benefit Analysis (CBA) to examine the monetized benefits relative to costs for the Usual Care Control and Incentive intervention conditions. The economic outcomes are health care utilization during the 2-year intervention evaluation period (see below). We expect that the Incentive Intervention will yield greater economic benefits relative to its costs than the Usual Care Control.

Measures assessed repeatedly over time will be analyzed with a longitudinal logistic regression model. Within-person correlated outcomes will be handled using generalized estimating equations (GEE; Zeger, Liang, & Albert, 1988). Measures assessed once will be analyzed using logistic regression. The magnitude of effects will be expressed using odds ratios with 95% CI. Intent-to-treat analyses will be adjusted for covariates used for stratification (Pocock et al., 2002). Two-sided tests with p-values <.05 will be considered significant.

- b. Statistical plan including sample size justification and interim data analysis.

STATISTICAL ANALYSES

Measures assessed repeatedly over time will be analyzed with a longitudinal logistic regression model. Within-person correlated outcomes will be handled using generalized estimating equations (GEE; Zeger, Liang, & Albert, 1988). Measures assessed once will be analyzed using logistic regression. The magnitude of effects will be expressed using odds ratios with 95% CI. Intent-to-treat analyses will be adjusted for covariates used for stratification (Pocock et al., 2002). Two-sided tests with p-values <.05 will be considered significant.

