Primary outcome analyses. We will fit a longitudinal logistic regression model $\text{logit}(Y_{ij}) = \beta_0 + \beta_1 tx + \beta_{2-6}x_{2-6} + \epsilon_{ij}$, where Y_{ij} is the presence of a detectable viral load for the i th person at the j th timepoint (8 visits over two years of treatment), β_1 is the covariate of interest representing the expected decrease in log odds of a detectable viral load as a function of assignment to the treatment group, and β_{2-6} are the coefficients for the 5 randomization covariates. Additional models with time and time by treatment interactions will be fit secondarily to assess time trends in treatment effect.

Secondary outcome analyses. We will fit analogous longitudinal logistic regression models for HRMS-verified ART adherence, self-reported adherence, prescription maintenance, and attendance at HIV medical care visits. We will assess post-treatment effects by fitting analogous models for each outcome, but using only data from the two post-treatment visits.

Moderator analyses. For the primary outcome, we will fit models with interactions between treatment and each of the 5 randomization covariates (drug dependence, alcohol dependence, TOFHLA total score, delay discounting, and Beck Depression score) to assess whether treatment effect varies as a function of the putative moderator. For example, for CIDI drug dependence, we would fit the model $\text{logit}(Y_{ij}) = \beta_0 + \beta_1 tx + \beta_{2-6}x_{2-6} + \beta_7 tx * \text{drug dependence} + \epsilon_{ij}$, where β_1 would represent the treatment effect (expressed as a difference in log odds of a detectable viral load between treatment and control groups) among individuals without drug dependence, and β_7 would represent the difference in treatment effect between individuals with and without drug dependence. All moderator analyses will be considered exploratory and will not be corrected for multiple comparisons. These variables will be examined as potential moderators because drug use (Mimiaga et al., 2013), health literacy (Kalichman et al., 2008),

and depression (Murphy et al. 2013) has each been associated with poor adherence to antiretroviral medications. Impulsivity will be assessed as a potential moderator because high levels of impulsivity have been associated with poor health decision making and adverse health behaviors (Axon et al., 2009; Bickel et al. 2014; Bradford et al., 2010).

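### Eight or nine secondary tests are each called significant at two-sided p<.05, with no order, adjustment or exploratory label among them

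*Combined protocol and SAP*

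**What the plan says.** The significance rule appears twice in section 7, at the end of the outcome definitions and again at the start of the statistical analyses: "Two-sided tests with p-values <.05 will be considered significant". Neither place separates the primary outcome from the others.

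The secondary outcome analyses in section 7b fit separate models for "HRMS-verified ART adherence, self-reported adherence, prescription maintenance, and attendance at HIV medical care visits". They then add: "We will assess post-treatment effects by fitting analogous models for each outcome, but using only data from the two post-treatment visits". The matching aim in section 7a covers "undetectable levels of viral loads, maintenance of antiretroviral prescriptions, consistent adherence to antiretroviral therapy, and retention in HIV care" once the incentives stop, and says: "We will assess measures described above but at the two 6-month assessments during the year after the intervention ends".

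The moderator paragraph in section 7b is handled differently: "All moderator analyses will be considered exploratory and will not be corrected for multiple comparisons". No such sentence is attached to the secondary outcomes.

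The opening of section 7 gives the plan's only general statement on limiting false positives, which is that "we identified one primary biological outcome measure and a limited number of secondary and economic measures". It adds no testing procedure for the secondary measures.

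**The concern.** Each secondary outcome is set out as a specific aim about the effectiveness of the incentives, and each falls under the same p<.05 rule as the primary. Because the plan labels the moderators exploratory and uncorrected, its silence on the secondaries cannot safely be read as giving them the same status. The plan also knows how to set a gate: its third mediation step is taken only if the first two succeed. It sets none for the secondaries.

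What is at stake is what the trial may claim. Under the rule as written, one nominal p<.05 among several tests could be reported as a significant effect on adherence or as a lasting effect, even if the primary or the post-treatment viral load result is null. The post-intervention aim is the more exposed. The abstract says that no treatment has yet produced effects that last after it ends, so such a claim would be notable, and no outcome is named as the one that decides it. The plan also leaves open whether post-treatment adherence is one test or two, so the size of the family is not fixed.

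**Working it through.** **Inputs from the documents**

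- Per-test level: .05, two-sided (section 7). This is the only error rate stated. It reproduces trivially for one test: 1 - 0.95 = 0.05.
- On-treatment secondary tests: 4, namely HRMS adherence, self-reported adherence, prescription maintenance and attendance.
- Post-treatment tests: viral load, prescriptions, adherence and retention make 4, or 5 if adherence is tested by both HRMS and self-report.
- Total: 4 + 4 = 8, or 4 + 5 = 9. Moderator, mediation and economic analyses are not counted.

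**Assumptions**

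- All the secondary nulls counted are true.
- The test statistics are normal with a common pairwise correlation r. The documents give no value. Section 7a says that patients must adhere and stay in care to reach undetectable viral load, so r is probably positive. The range 0 to 0.9 is shown.

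**Formulas** for the chance of at least one false significant result among k tests

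- Independent tests (r = 0): 1 - 0.95^k. For example, 1 - 0.95^4 = 0.1855 and 1 - 0.95^9 = 0.3698.
- Correlated tests: 1 - ∫ φ(t) [Φ((c - √r·t)/√(1-r)) - Φ((-c - √r·t)/√(1-r))]^k dt, with c = 1.96, by numerical integration.

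**Results**

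| Family | r = 0 | r = 0.3 | r = 0.5 | r = 0.7 | r = 0.9 |
|---|---|---|---|---|---|
| 4 tests (on-treatment, or post-treatment with one adherence test) | 0.186 | 0.174 | 0.156 | 0.130 | 0.094 |
| 5 tests (post-treatment with both adherence tests) | 0.226 | 0.209 | 0.183 | 0.148 | 0.102 |
| 8 tests | 0.337 | 0.300 | 0.250 | 0.191 | 0.119 |
| 9 tests | 0.370 | 0.326 | 0.269 | 0.202 | 0.124 |

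A common correlation is a simplification. Simulations with weaker correlation between different outcomes in different periods gave 0.22 to 0.34 for 8 or 9 tests, inside the same range. One example used 0.5 within a period, 0.5 for the same outcome across periods and 0.3 otherwise; it gave 0.267 for 8 tests.

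The table counts false results in either direction. Counting only those that favour the incentives, at r = 0.5, the rates are 0.078 (4 tests), 0.091 (5) and 0.135 (9), against 0.025 for one test.

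**The case against.** There is a fair case for leaving the plan alone.

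- **There is already a hierarchy at the top.** One primary outcome is named, and power is calculated for it alone. The secondaries are introduced tentatively, as measures that the intervention does not target directly. Many trials leave such outcomes unadjusted and report estimates with confidence intervals. This stands as a defence of not adjusting. It does not cover calling each result significant at p<.05 without stating its status.
- **The plan promises no family-wise 5%.** A reader might infer that a stated 5% guarantee is broken. The documents do not support that: .05 is a per-test rule, and each single test keeps it.
- **No single figure is established.** A reader might settle on 25-27%. That holds only for 8 or 9 tests at r = 0.5, which is not in the documents. Pooling both periods is also a choice, because the plan sets them out as separate objectives. Taken separately, the families run from 9% to 23%.
- **No rule says that one significant result proves an aim.** The post-intervention measures are listed together. That a single result could carry the aim follows from the absence of a rule, not from a stated one.
- **The all-null case is the worst case.** If the incentives do suppress viral load, the adherence nulls are unlikely all to be true, and fewer true nulls remain to be rejected falsely. This stands, so the figures are upper values for each r. They apply most directly to the post-treatment family, where a complete null is plausible: the background reports that effects in earlier incentive studies did not last.

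**Conclusion.** The gap is real but limited. The plan gives no order, adjustment or label for 8 or 9 secondary tests that are each called significant at p<.05. If all the nulls in a family are true, the chance of at least one false claim is about 9-19% for the 4 on-treatment tests, 9-23% for the 4 or 5 post-treatment tests and 12-37% for all 8 or 9, for a common correlation from 0.9 down to 0. At every value in that range the rate exceeds .05, so the conclusion does not depend on the unknown correlation; only its size does.

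A reader might go further and infer that the main conclusion of the trial is at risk. It is not: the primary treatment coefficient is one test at .05, and nothing here changes it. The point concerns what may be claimed from the secondary and post-treatment results.

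**What to change.** In the statistical analyses of section 7b, and where the rule is repeated earlier in section 7:

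1. Limit the p<.05 significance rule to the treatment coefficient of the primary model.
2. State that all secondary and post-treatment outcomes are supportive and not corrected for multiple comparisons, as the plan already does for the moderators, and that they are reported as odds ratios with 95% CIs and no significance claim.
3. Name undetectable viral load at the two post-treatment visits as the main outcome for the post-intervention aim.
4. Say whether post-treatment adherence is one test or two.
5. Note that the mediation analysis may keep statistical significance for adherence as its own entry condition, without that being a secondary claim.

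If the sponsor wants confirmatory secondary claims, it can instead replace step 2 with a standard procedure such as Holm, applied within the on-treatment family and within the post-treatment family and entered only after a significant primary. That holds each family at 5%, so at most 5% + 5% = 10% across both. It must be fixed before outcomes are seen by group. The COVID-19 section speaks of remaining assessments, which suggests late follow-up; if that point has passed, the supportive label is the sound choice.

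A fixed sequence across both periods is not needed. Placing a post-treatment test early could block on-treatment aims for an unrelated reason, since the background suggests that effects may fade.

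The cost is a few sentences, with no new data, visits or participants. The downside is that some secondaries with nominal p<.05 could not be claimed as significant; their estimates and intervals are still reported.

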Participants (N = 200) who complete the HIV Medical Care Education program will be randomly assigned to a Usual Care Control group or the Incentive group. A computerized urn randomization procedure (Wei & Lachin, 1988) will be used to balance groups on five baseline characteristics that may influence outcome: (1) opiate or cocaine positive urine sample at intake to the study (Y/N); (2) Self-reported use alcohol to intoxication on 20 or more days in the past 30 on the ASI (Y/N); (3) health literacy as assessed on the TOFHLA (score \leq the rolling median, Y/N); (4) impulsivity as assessed by delay discounting (k value from the raw discounting data for each participant, which is an index of impulsivity (\leq the rolling median of k, Y/N); and (5) depression as assessed by the Beck Depression Inventory (score \leq the rolling median, Y/N). Participants will be stratified by DSM V cocaine, opiate and alcohol dependence, health literacy, and depression at intake because drug use (Mimiaga et al., 2013), health literacy (Kalichman et al., 2008), and depression (Murphy et al. 2013) has each been associated with poor ART adherence. Participants will be stratified based on measures of impulsivity because high levels of impulsivity have been associated with poor health decision making and adverse health behaviors (Axon et al. 2009; Bickel et al. 2014; Bradford et al., 2010). Participants will be taught the details of their group with written instructions and quizzes. Participants will earn up to about \$15 for answering questions on the quiz.

Incentive Group

The Incentive group will receive the novel empirically-based incentive intervention to promote long term suppression of HIV-1 RNA (viral load) being evaluated in this study. The incentive intervention will employ features and parameters that have been shown critically important to promote therapeutic behavior change in drug users and other populations (Higgins et al., 2008; Lussier et al., 2006; [name] et al., 2011). Participants will be taught the details of the incentive program with written instructions and quizzes.

A Prescription for ART. When a participant gets assigned to the Incentive group, he/she will be asked if he/she has a current prescription for ART and if he/she has at least a 2-day supply of medication. As described below, blood draws and the incentive program described below will not begin until the participant has an active ART prescription and has at least a 2-day supply of medication.

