Intake Only Assessment Instruments. At intake we will administer: 1) BDI to screen for depression (Beck et al. 1993). 2) Test of Functional Health Literacy in Adults (TOFHLA) to measure health literacy (Parker et al., 1995). 3) A computer delay discounting task to assess impulsivity (Johnson and Bickel, 2002). In this task, on each trial the participant makes a choice between a smaller immediate reward option (e.g., \$5 now) and a larger \$10 reward delivered after a given delay (e.g., 1 week). The magnitude of the smaller immediate reward is adjusted across trials to determine an indifference point, or the amount of immediate money equal to the delayed \$10. Once an indifference point is detected, the task moves to the next of four delays (1 day, 1 week, 1 month, 6 months); 4) The Addiction Severity Index; 5) The Wide Range Achievement Test.

Intake, 3-Month and 6-month Follow-up Assessments. We may conduct these assessments at all time points: 1) HIV-1 RNA (viral load) in blood by Maryland DHMH Laboratories. 2) The presence or absence of 15 ART medications in blood (Marzinke et al., 2014). 3) We may assess blood samples that we collect for the quantitative levels of antiretroviral medications or their metabolites to determine if participants are maintaining the presumed therapeutic blood levels of the antiretroviral medications. The assessments of quantitative blood levels of antiretroviral medications could provide more information than the qualitative tests. For example, a participant could test positive for an antiretroviral medication on the qualitative test by taking the medication occasionally, but not take the antiretroviral medication often enough to maintain therapeutic blood levels of the medications. 4) blood tests of CD4 counts; 5) urine tests of drugs of abuse. 6) A

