Mediation analysis. We will assess potential mediating effects of medication adherence as assessed by qualitative blood testing on viral load using the method of Baron and Kenny (1986). Specifically, this involves estimation of (1) the effect of treatment assignment (incentives) on undetectable viral load without controlling for medication adherence, (2) the direct effect of incentives on medication adherence, and if these two steps yield clinically and statistically significant effects, 3) the effect of incentives on viral load after controlling for medication adherence ($\text{logit } (Y_{ij}) = \beta_0 + \beta_1 x_i + \beta_{2-6} x_{2-6} + \beta_7 \text{adherence} + \epsilon_{ij}$). If medication adherence does mediate the effect of the incentives on presence of a detectable viral load, in this final model we would expect the effect of treatment (β_1) to be attenuated relative to the step 1 model, and for adherence (β_7) to be a clinically and statistically significant predictor of presence of a detectable viral load.

Missing data. We expect to collect $\geq 80\%$ of 3-month assessments (see below). Our primary approach will be to impute all missing values as the adverse outcome (e.g., detectable viral load). Model parameter estimates from this approach will be compared to a method without imputation. If these methods yield differing results, conclusions will need to be tentative. To investigate sensitivity to missing values, participants with and without missing values will be compared by covariates and treatment assignment.

ECONOMIC ANALYSES

We will use the provider perspective using a modified SASCAP and the research team's financial records. Intervention activities will be captured with the modified Economic Form 90 AIR/ED.

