The primary outcome measure of undetectable viral loads will be analyzed with a longitudinal logistic regression model using GEE (Diggle & Diggle, 2002). We used Liu and Liang (1997) to determine the total N required to detect a difference between groups with 80% power. The adjacent figure shows the total number of participants (N) required to detect a difference of 15% between the Usual Care Control and the Incentive Group at the eight 3-month assessments during the intervention evaluation period. The figure shows different percentages for the Usual Care Control group because that value affects the sample size required. 15% is smaller than the effects produced in all prior studies of voucher reinforcement of cocaine or opiate abstinence or medication adherence and smaller than all effects produced by the Therapeutic Workplace and smaller than the incentive effects in promoting drug abstinence, medication adherence and other health behaviors as shown in three different meta-analyses (Petry et al., 2012; Prendergast et al. 2006; Lussier et al., 2006). The horizontal red lines show the number of participants planned based on the number of participants enrolled and randomized to the two groups without (top dashed line) and after adjusting for the anticipated rates of missing data (20% missing, bottom solid red line). Based on this analysis, we need to enroll and randomize 200 participants (horizontal dashed line) to ensure that we have sufficient sample sizes after adjusting for the rates of missing data. After adjusting for missing data (20% missing), this would yield a sample size of 160 participants (200 participants x 0.80 collected samples = 160 participants). The adjusted sample size of 160 participants (solid red line) is a little more than the maximum number of participants that would be required.

c. Early stopping rules.

The protocol can be stopped based on recommendations of the Scientific Advisory Committee overseeing this study. We will ask the Scientific Advisory Committee to recommend that the trial be stopped if a review of the adverse events suggests to any of the investigators that the number of related and unexpected adverse events is unacceptably high. The Scientific Advisory Committee will be allowed to request statistical analyses to compare the groups on the rates of different adverse events or to have the adverse event data summarized in other ways that they deem appropriate.

Risks

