a. Medical risks, listing all procedures, their major and minor risks and expected frequency.

There is essentially no risk above those of normal daily living associated with the incentives, or with the data collection procedures used in these studies.

Blood samples will be collected from participants in the Incentive group. Those participants will provide a maximum of 1 blood sample per week. The samples will be tested for viral load and will involve collecting up to 10 cc of blood per sample. Participants in both groups will provide blood samples every 3 months for the primary and secondary outcome measures. Each of those samples (25 cc in total) will be tested for viral load (10 cc), for the presence of antiretroviral medications (5 cc), and for CD4 Counts (10 cc). Taking blood may cause some discomfort, bleeding or bruising where the needle enters the body, and in rare cases, it may result in fainting. There is a small risk of infection. When possible, we will use data available in each participant's medical records to get recent viral load and CD4 counts measures instead of collecting blood samples at each assessment time point.

b. Steps taken to minimize the risks.

To protect confidentiality, all research participants are identified by participant identification codes (Participant IDs) consisting of their initials and sequentially-assigned participant numbers on most forms and data files, and not by their names. Picture ID cards are maintained by staff in a locked container, and kept in a locked, secured area when not in use. All research data are stored in locked areas accessible only to research staff and are not left unattended. Documents with confidential information are shredded before being discarded. Confidential information is never given to anyone outside of the research program without the explicit written permission of the research participant. Only selected designated staff members are approved to give confidential information out after obtaining explicit written permission from the

participant. All research staff are trained in these procedures. We collect only general information about participant activities, legal and illegal. We do not collect information about specific illegal acts. To further protect confidentiality, we will obtain a confidentiality certificate from NIH to protect data collected in this study.

c. Plan for reporting unanticipated problems or study deviations.

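### The primary model omits quantitative intake viral load: the test stays valid, but a chance imbalance would go uncorrected and some power may be lost

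*Combined protocol and SAP*

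**What the plan says.** Section 4a, Experimental Design: an urn procedure "will be used to balance groups on five baseline characteristics that may influence outcome". These are opiate- or cocaine-positive urine, frequent drinking to intoxication, health literacy, delay discounting and depression score. Viral load is not among them.

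Section 7, under both the outcome measures and Statistical analyses: "Intent-to-treat analyses will be adjusted for covariates used for stratification". The primary model in section 7b follows this rule. It has an intercept, treatment and five terms whose betas "are the coefficients for the 5 randomization covariates". The secondary, post-treatment, moderator and mediation models keep the same five terms, and none adds intake viral load.

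The value should nevertheless exist. Section 5 admits only applicants with viral load above 200 copies/mL. The list of intake and follow-up assessments in section 4a begins with "HIV-1 RNA (viral load) in blood by Maryland DHMH Laboratories", although that list is introduced as assessments that may be done. Two other places allow a different source. The Initial Screening Interview text uses released clinic records to establish eligibility, and the Risks section says staff will, when possible, use "medical records to get recent viral load and CD4 counts measures instead of collecting blood samples at each assessment time point".

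**The concern.** The primary outcome is viral load dichotomised at 200 copies/mL. Everyone enters above that threshold, so the binary status at entry is constant and carries no information. The quantitative intake value does vary, and it is the pre-randomisation measurement of the quantity that is later dichotomised. It is an obvious candidate for adjustment, yet it is neither balanced by design nor used in analysis.

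Two things are at stake. First, if intake viral load predicts later suppression, leaving it out costs some power. Second, if the arms differ on it by chance, the planned estimate is pulled up or down and no planned analysis shows by how much. Readers will look for such a difference in the baseline table, and a covariate chosen after the results are seen would not be credible. Because the plan never uses a baseline viral load, it also does not say which result would count as one: the intake sample or a clinic record.

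**Working it through.** **1. The plan's own figure.** Section 7b, Power analysis, gives 200 x 0.80 = 160 participants after 20% missing data, which checks. It says that 160 "is a little more than the maximum number of participants that would be required" for 80% power to detect 15 points over eight visits. The within-person correlation rho is not in the text and the figure is not shown, so I solved for it, treating 160 as the maximum and assuming 1:1 allocation:

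N = 2(1.96 + 0.8416)² [pc(1−pc) + pt(1−pt)] / 0.15² x (1 + 7rho)/8

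This is largest at pc = 0.425 and pt = 0.575. The single-visit N is then 2 x 7.849 x 0.48875 / 0.0225 = 341. Setting 341(1 + 7rho)/8 = 160 gives rho = 0.393. A slightly different two-proportion formula gives a single-visit N of 348 and rho of 0.383.

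**2. Chance of imbalance.** The standard error of the arm difference in standardised baseline is sqrt(2/100) = 0.141 SD. P(|difference| > 0.2 SD) = 2[1 − Φ(0.2/0.141)] = 0.157, or about 8% in each direction.

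**3. Simulation.** Data came from a random-intercept logistic model with rho = 0.39, 200 randomised, eight visits and 57.5% vs 42.5% suppressed. A random 20% of values were missing and counted as detectable, as the Missing data paragraph plans. The observed suppression rates become 0.8 x 0.575 = 0.46 and 0.8 x 0.425 = 0.34, so the log odds ratio is ln(0.46/0.54) − ln(0.34/0.66) = 0.50. Analysis was logistic GEE with robust standard errors, 4,000 runs per scenario (3,000 for type I error). The five urn factors were left out of both models. The prognostic strength is an assumption and acts at all visits.

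Power (%), without / with baseline log10 viral load:

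| Odds of suppression per SD | Average over trials | 0.2 SD higher in Incentive arm | 0.2 SD lower in Incentive arm |
|---|---|---|---|
| x 0.86 | 82.3 / 82.4 | 78.2 / 82.5 | 87.0 / 83.5 |
| x 0.75 | 83.6 / 84.5 | 74.7 / 83.0 | 89.5 / 84.3 |
| x 0.59 | 83.7 / 87.9 | 70.0 / 87.6 | 94.0 / 87.2 |

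Mean log odds ratio without the covariate:

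| Odds per SD | Average | 0.2 SD higher | 0.2 SD lower |
|---|---|---|---|
| x 0.86 | 0.498 | 0.476 (4% smaller) | 0.532 (7% larger) |
| x 0.75 | 0.505 | 0.452 (10% smaller) | 0.552 (9% larger) |
| x 0.59 | 0.507 | 0.424 (16% smaller) | 0.589 (16% larger) |

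- Standard error: 0.173 without the covariate, 0.171–0.174 with it.
- Type I error: 5.2–5.4% without, 4.8–5.4% with. Under no effect and a 0.2 SD imbalance favouring the Incentive arm, rejection is 5.1%, 5.1% and 6.2% without and 4.8–5.0% with.
- Check at N = 160 with complete data: 79–80% without the covariate, in line with the plan's 80%; 79%, 81% and 84% with it.

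**4. The one mechanism in the documents.** Section 4a expects a fall of at least 0.15 log per week on consistent ART. Over 13 weeks, a start above 200 x 10^(13 x 0.15) = 17,825 copies/mL would still be detectable at month 3. With that as the only link (assumed log10 mean 4.2, SD 0.9), power is 81.6% without and 81.5% with the covariate: no gain, because essentially only one visit is affected.

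**5. Independent run.** N = 160, complete data, rho = 0.385, five non-prognostic stand-ins for the urn factors in both models. For odds ratios of detectable viral load of 1.25, 1.5, 2.0 and 3.0 per SD, power is 79% vs 79%, 79% vs 82%, 78% vs 87% and 78% vs 95%. In the tenth of trials with the imbalance most against the Incentive arm, the first three become 73% vs 80%, 62% vs 79% and 49% vs 86%.

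**The case against.** The plan contains no error here. It adjusts for the factors it balances on, and the test holds its size. That stands, and it is why the point is minor.

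The benefit depends on a prognostic strength the documents do not supply, and their only stated mechanism yields nothing. That also stands. The size of the gain follows the assumption, and with a weak link it is nil. But in that case the covariate also costs next to nothing (82.3% vs 82.4%).

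The main simulation omitted the urn factors, which may correlate with intake viral load. With them in the model, at the strongest of the three assumed effects, the gain is 5 points if they explain none of viral load, 4 if they explain 20% and 2 if they explain 40%. If the urn balanced them perfectly, the 16% chance of imbalance would fall to 11% and 7% in the latter two cases. These shares are themselves assumptions. The gain shrinks modestly but does not vanish.

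The imbalance figures are conditional, and the planned standard error already covers such variation across trials. This is correct: the planned confidence interval is honest on average, but it cannot correct the particular trial.

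Finally, the COVID-19 paragraph in section 4a refers to completing the remaining assessments of an unblinded trial, so changing the primary model late could itself look data-driven. This limits when the change can be made, not whether it is sound.

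**Conclusion.** The concern holds as a minor point of efficiency and protection against imbalance, not of bias or validity. The average gain from adjustment is 0 to 4 power points over the assumed range of 0.86 to 0.59 per SD, and larger only if the link is stronger than that. In the roughly one trial in six with an imbalance above 0.2 SD, the consequence is greater. At exactly 0.2 SD, the planned log odds ratio is about 4–16% too small or 7–16% too large, depending on direction and prognostic strength.

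These figures rest on an assumed prognostic strength that is constant over visits, a correlation inferred from the stated 160, 1:1 allocation, data missing at random visits, and urn factors unrelated to intake viral load. Confidence is medium. The omission is plain in the text; its size is not.

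**What to change.** Add to section 7b:

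> The primary model, and the analogous viral-load model for the two post-treatment visits, will also adjust for baseline log10 viral load as a continuous covariate. Baseline is the last value before randomisation, taken from the intake sample or, failing that, from the medical record used to establish eligibility.

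Report the model with only the five randomisation factors as a sensitivity analysis. Date the change and make it before any outcome data are compared by arm. If that comparison has already been made, keep the planned model as primary and report the adjusted one as supplementary.

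The cost is two sentences, one model degree of freedom, and recording the source and date of each baseline value. The odds ratio becomes conditional on baseline viral load and is not identical to the planned one: the simulated mean log odds ratio is 0.50–0.51 without the covariate and 0.50–0.53 with it. The post-treatment model was not simulated; it is included for consistency.
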